Isoprostanes are stable oxidative products of polyunsaturated fatty acids. Oxidative stress will be evaluated by following serum isoprostane levels over the course of dose escalation and by assaying csf isoprostane before and after R(+)PPX. A very sensitive LC-MS assay will be used. Serum and CSF PPX levels will also be assayed by LC-MS. To assess change in isoprostane levels with treatment, we will compare baseline (pre-treatment) and 6-month (post-treatment) isoprostane levels using a paired t-test. We hypothesize that isoprostane levels will be reduced after 6 months of R(+)PPX treatment.

2-FDG PET

Changes in cerebral glucose metabolism as a proxy for mitochondrial respiration will be assayed at baseline and after a period of several months dosing with R(+)PPX at 300 mg/day. Multiple regions will be compared, with particular attention paid to hippocampus. The statistical mapping approach described by Chen, et al [31] will be used. Regional FDG uptake will be compared pre- and post-PPX dosing. Correlations will also be sought with assays of oxidative stress reduction, to see if greater reductions in brain oxidative stress (reflected by reductions in isoprostane levels) are reflected in elevations in cortical 2-FDG.

Conclusions

An abundance of compelling evidence supports the early appearance of oxidative stress as a pathogenic event in AD. Oxidative stress is elevated in brains of persons with pre-AD condition of MCI and in transgenic mice expressing familial AD genes prior to the amyloidosis seen in these models. Our

studies in the mitochondrial transgenic cybrid model of AD supports mtDNA as a contributor to AD oxidative stress and beta amyloid production. *In toto*, reduction of oxidative stress early in the course of AD should reduce the trajectory of neurodegeneration.

The sponsor studied S(-) and R(+) PPX in his laboratory beginning in 1997 and has clinically tested R(+) pramipexole in ALS subjects under a physician-sponsor IND since 2004. R(+)PPX is now commercially licensed and under separate development for treating ALS by Knopp Neurosciences. R(+)PPX is a brain and mitochondrially concentrated antioxidant that can be safely administered to humans at daily doses up to 300 mg/day and has no detectable DA receptor activity *in vivo*. At this dose many subjects achieved trough steady-state PPX levels of >1 μ M, predicting brain levels of >6 μ M that are clearly in the ROS scavenging and neuroprotective levels. R(+)PPX at 300 mg/day substantially improves the course of ALS in short-term studies and will enter Phase 3 testing later this year.

The present application seeks to introduce R(+)PPX treatment to subjects with early AD. In this protocol the subjects will undergo careful dose escalation from 100 mg/day to 300 mg/day R(+)PPX over 4 months. Subjects will have regular serum, combined with baseline and late treatment spinal fluid samples, assayed for isoprostanes as measures of oxidative stress. Serum and spinal fluid will also be assayed for [PPX]. As a measure of cerebral metabolism, brain 2-FDG PET scans will be obtained at baseline and after several months of dosing with 300 mg/day R(+)PPX.

The goal of the present study is to determine if R(+)PPX can be administered in high doses to probable AD subjects, and if so, whether oxidative stress is reduced and cerebral metabolism is increased. Hopefully the results from this study will justify the cost of a larger early efficacy study in probable AD.

Data Management

The KU Alzheimer and Memory Program currently uses an electronic database system, called REDCap (Research Electronic Data Capture), for much of its data management needs. REDCap was developed by Vanderbilt University, with collaboration from a consortium of institutional partners, for electronic collection and management of research and clinical trial data. This secure system is hosted by the Center for Research Methods and Data Analysis (CRMADA) at the University of Kansas Lawrence (KU-L) campus. The CRMADA hosts a KU-L Information Technology-controlled, HIPAA-certified REDCap database server on which project data will be stored. The REDCap system provides secure, web-based applications that have an intuitive interface for users to enter data and real time validation rules (with automated data type and range checks) at the time of entry. These systems offer easy data manipulation with audit trails and an automated export mechanism to common statistical packages (SPSS, SAS, Stata, R/S-Plus). REDCap was developed specifically around HIPAA-Security guidelines and all web-based information transmission is encrypted. REDCap is used at many institutions and currently supports > 170 academic/non-profit consortium partners on six continents and 13,000 research end-users (www.project-redcap.org). [name], a member of the Alzheimer and Memory Program at KUMC, is responsible for working with the CRMADA and the REDCap system to design the database, its forms, the data entry process, and reports related to adverse events and pertinent safety data for this research study.

Data Safety and Monitoring Plan

All adverse events (AE's) will be reported to the PI and sponsor in a timely fashion. The study coordinator will enter the AE data from the source documentation into REDCap within 5 business days from receipt of the initial call to report the AE. Any serious adverse event will be reported to the PI and sponsor immediately and then to the General Clinical Research Center and the Human Subject's Committee according to reporting guidelines.

A Data Safety and Monitoring Board (DSMB, see DSMB charter attached below) will meet quarterly to review AE's and the overall safety of the ongoing trial. The DSMB is composed of three experienced clinicians: [name] from the Robert Wood Johnson Medical School, [name] from

the University of Chicago, and [name] from the University of Virginia. [name] will be the acting Chairman.

The DSMB will have access to de-identified participant medical records and other study-related records. The investigator agrees to cooperate with the monitor (s) to ensure that any problems detected in the course of these monitoring visits are resolved. Personal contact between the DSMB and the investigator will be maintained throughout the clinical trial to assure that the investigator is fulfilling his obligations and the facilities used in the clinical trial remain acceptable.

The DSMB will perform a quarterly review of lab safety data, results of physical/ neurological assessments and subject adverse event/SAE reports. The DSMB can advise and recommend temporary or permanent withdrawal of a subject or that the entire study be placed on hold or terminated.

All grade 2 and above AE's according to CTCAE v3.0 will be reviewed by the DSMB members quarterly. To facilitate this review, a list of each AE grade 2 or higher (by CTCAE v3.0) will be generated from REDCap. Each AE listed will include the grade, the type of event, and the potential relationship of the AE to the study intervention. The PI will be notified within 24 hours by the study coordinator of all AE's grade 3 or higher. Should a study participant experience an AE in any category rated 3 or greater according to CTCAE v3.0, that individual will be removed from the study immediately. Should three or more subjects (15% of target enrollment) have AE's in any category that is grade 3 or higher according to CTCAE v3.0 that are possibly or probably related to study intervention, the study will be terminated.

Schedule of Study Procedures and Assessments

Week #	-4	-2	0	2	4	6	8	10	12	14	16	18	20	22	24	26
Visit Name	Scr	B	1	P/C	P/C	P/C	2	P/C	P/C	P/C	3	P/C	P/C	P/C	4	EOS
Informed Consent	X															
NINDS-ADRDA	X															
Hachinski Ischemic Scale	X															
Geriatric Depression Scale	X															
MMSE	X															
Demographics	X															
Medical History	X	X														
Medication History	X	X														
Body height/ weight *	X		X				X			X				X	X	
Vital Signs	X		X				X			X				X	X	
Baseline Sx Checklist	X		X				X			X				X	X	
Physical/Neuro Exam	X						X			X				X	X	
Safety labs	X						X			X				X	X	
Inclusion/ Exclusion	X															
ADAS-Cog		X					X			X				X		
FDG PET scan-brain		X													X	
Lumbar puncture		X													X	
Isoprostane analysis **		X													X	
Dispense Study Drug			X				X			X						
Drug Accountability				X			X			X					X	

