R(+)PPX slows the progression of disability and decline of respiratory capacity in early ALS subjects (Knopp Phase 2b, Phase 3 pending). The scientific rationale for the current proposed study in probable AD is that oxidative stress is an early abnormality in human AD and transgenic animal models of familial AD. Increased brain oxidative stress is likely causal for AD pathogenesis and can stimulate net production of beta amyloid by increasing beta amyloid synthesis (beta secretase expression) and inhibiting beta amyloid degradation (neprilysin activity). The sponsor's group has shown that mtDNA from AD subjects expressed in a cybrid model can drive increased oxidative stress and beta amyloid production, which is reduced by PPX. The current study will not define how oxidative stress is increased in AD brain, rather it will correct that problem by treatment with a well tolerated and novel mitochondrial antioxidant.

The sponsor has extensive experience testing R(+)PPX in ALS and has an active physician-sponsor IND that has been amended to allow testing of R(+)PPX in AD subjects (see DSMB charter in appendix for more information). Because of conflicts of interest, the sponsor will not be involved at all in recruitment, treatment or evaluation of AD subjects; that will occur at Kansas University Medical Center (KUMC), with [name] as the Principal Investigator. [name],MD, PhD will function as Sponsor in this study but will have no direct involvement in clinical care.

The primary goal of the study is to establish the safety and tolerability of the study medication in individuals with AD. Exploratory variables involve changes in brain and peripheral oxidative stress assayed by isoprostanate levels in spinal fluid and serum, respectively, change in cognitive function and improvement in brain glucose metabolism assayed by FDG-PET scan. The goal of the present study is to establish that up to 300 mg/day of R(+)PPX is tolerated by subjects with probable AD, lowers oxidative stress and may show a trend of improving brain glucose metabolism.

Subject selection and recruitment

Subjects with probable AD will be identified and recruited through the Memory Disorders Clinic at the University of Kansas Medical Center (KUMC). This clinic is under the direction of [name], an accomplished AD clinical investigator.

KU Alzheimer and Memory Program

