Since initiating the database in September 2004, information on a total of 945 unique patients has been entered into our database. Of these, 486 were diagnosed with AD (mean age 74.7 years, MMSE 19.8, and logical memory II 1.5) and 112 were diagnosed with MCI (mean age 72.5, MMSE = 26.8, logical memory II = 5.1). Forty patients included in the database have a diagnosis of dementia with Lewy bodies and 25 with frontotemporal dementia. The use of the database has been helpful in identifying participants for recruitment into research studies. Patients identified as potentially meeting enrollment into the UDS Registry or clinical trials are flagged in the database and referred to our recruitment coordinator for contact and further screening. The database has been an effective and efficient way to recruit participants from our active clinic population.

Alzheimer's Disease: Individuals with AD meet NINDS-ADRDA criteria for possible of probable AD and have a score of 14 - 26 inclusive on the MMSE. NINDS-ADRDA criteria are operationalized as 1) memory impairment, 2) the gradual onset and progression of impairment in memory and in at least one other cognitive domain (as demonstrated by clinical history and neuropsychological testing) and 3) the absence of clinical or laboratory evidence of other disorders that could account for memory or cognitive decline or if a second disorder is present it is not considered the primary cause of dementia.

VCU laboratory site

The physician-sponsor is a faculty member at Virginia Commonwealth University and has no relationship with [name] or KUMC. Because the /sponsor has a financial interest in the commercial development of R(+)PPX, it is critical that he have no relationship with [name]/KUMC and have no influence on subject recruitment or study execution. However, the sponsor will provide analytical services for this application. Serum and spinal fluid specimens will be analyzed blinded as to subject identity and time in study. The sponsor has available facilities for LC-MS analysis of PPX and isoprostane levels.

Inclusion and Exclusion Criteria at Entry	
Inclusion Criteria	Exclusion criteria

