Positron Emission Tomography (PET) Scans: Fluoro-deoxy-glucose (FDG) PET imaging will be performed on all participants at baseline and after treatment for 6 months. Participants will be asked to fast for at least four hours prior to the scanning session. The participant's blood glucose will be checked prior to scanning and must be < 180 mg/dL. After the injection of 5 mCi of tracer, subjects will sit in a quiet, dimly lit room for 30 minutes after which they are placed in the scanner. Procedures will be identical to those used extensively by this group in the Alzheimer's Disease Neuroimaging Initiative.

Lumbar Puncture: Participants will arrive in the GCRC in the early morning after an overnight fast for blood and CSF collection. Fasting blood (14 cc) will be drawn for isoprostane analysis. [name] will perform all lumbar punctures. Lidocaine will be used for topical anesthesia and an atraumatic 24 gauge Sprotte needle will be inserted for CSF collection at the L3/4 or L4/5 interspace. 2 cc of fluid will be discarded and 2 cc sent to the local laboratory for routine cell counts, protein, and glucose. Ten milliliters of blood will be collected and spun. The serum sample will be sent to the protocol investigator for isoprostane analyses. After completion of the procedure, participants will be remain in the GCRC; have breakfast; and rest for about 30-45 minutes before being discharged home with post lumbar puncture instructions. A phone call to the participant 24 hours after the lumbar puncture will be performed to assess for any problems following this procedure. The FDG Pet Scan and the lumbar puncture must be completed on two different days at least 24 hours apart.

Safety Visits: Participants will have in-person safety assessments (1.5 hours) in the GCRC every 8 weeks. Vital signs and weight will be measured; concurrent medications and adverse events will be assessed. A physical and neurological examination will be performed by a study clinician. A targeted symptom checklist will be reviewed with the participant and study partner at each visit to assess occurrence of adverse events including those most associated with the use of pramipexole (Mirapex, see table 1 of appendix). Blood and urine will be collected for safety labs. Study drug will be dispensed at safety visits i.e. visits 1, 2, and 3. Cognitive testing (ADAS-Cog) will be administered at each safety visit.

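### Scan order is not masked in the FDG-PET analysis, which leaves a modest, unquantified risk of expectation bias in an exploratory outcome

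*Combined protocol and SAP*

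**What the plan says.** All references are to the combined protocol and SAP.

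- **Fluid assays (VCU laboratory site).** The section declares the sponsor's financial interest, requires separation from the clinical site, and then gives the sponsor the laboratory work. The next sentence reads: "Serum and spinal fluid specimens will be analyzed blinded as to subject identity and time in study". This is the only masking provision for any outcome measure.
- **Naming of the variables (Experimental Design and Methods, General).** The fluid variables are introduced neutrally: "Exploratory variables involve changes in brain and peripheral oxidative stress". The PET variable is "improvement in brain glucose metabolism assayed by FDG-PET scan". The stated goal adds that the drug "may show a trend of improving brain glucose metabolism", and the Conclusions section asks "whether oxidative stress is reduced and cerebral metabolism is increased".
- **Scan acquisition (Positron Emission Tomography Scans).** "PET imaging will be performed on all participants at baseline and after treatment for 6 months". The paragraph sets fasting, a glucose limit, tracer dose and uptake time, and ends: "Procedures will be identical to those used extensively by this group in the Alzheimer's Disease Neuroimaging Initiative".
- **Scan analysis (Exploratory Aims, 2-FDG PET).** The mapping approach of a cited neuroimaging study is to be used. The section also says: "Multiple regions will be compared, with particular attention paid to hippocampus". Uptake is compared before and after dosing, and correlations with the fall in isoprostanes are sought.

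No PET section says who processes the scans, or that they are processed without knowledge of their order.

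**The concern.** There is one treated group and each participant has two scans. Anyone who knows the scan dates knows which scan is on drug, and the text says which direction is hoped for. Decisions on registration, on excluding a scan from analysis and on extra regions could lean that way without anyone intending it.

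The plan already accepts that knowledge of time in study is worth guarding against for an instrumental assay. Regional image analysis can leave at least as much room for judgement. The FDG change is then set against the isoprostane change, so one member of that pair is masked and the other is not.

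What is at stake is the proof-of-concept reading. The Conclusions section hopes that the results will justify a larger efficacy study, and PET is part of that case.

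**Working it through.** **1. Is masking of scan order stated anywhere?** The treatment overview, the PET paragraph, the end-of-treatment assessments, the 2-FDG PET analysis, the Conclusions and the schedule of procedures all mention the scans. None mentions coding or masking. The sentence on neuroimaging-initiative procedures closes a paragraph on acquisition and cannot be read as a masking provision.

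**2. How much judgement is left?** The 2-FDG PET section commits to a mapping approach. The title of reference 31 describes a region of interest fixed in advance, and the Figure 7 legend says that the maps came from a training set. Both narrow the discretion. The same section then adds several regions and singles out hippocampus, with no list of regions and no rules for registration checks or scan exclusion. That is the opening that remains.

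**3. Can the risk be sized?** The plan gives no test, alpha, power or SD for PET in this trial, so there is no figure to reproduce. The paired t-test in the plan is specified for isoprostanes only. What follows is illustration on these assumptions: paired t-test, two-sided 5%, n = 20 (Specific Aims), and an upward shift s from order-aware processing, in SDs of the paired change.

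With true decline D in the same units, the noncentrality is (s − D) × √20, df = 19, critical value 2.093. The chance of a significant rise is the upper tail of that noncentral t.

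*No underlying decline (D = 0):*

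| s | noncentrality | significant rise |
|---|---|---|
| 0 | 0 | 2.5% |
| 0.1 | 0.447 | 6.2% |
| 0.2 | 0.894 | 13.3% |
| 0.3 | 1.342 | 24.6% |

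*Underlying decline from the plan's own background.* The section on early oxidative stress and cortical metabolism cites 66 subjects per arm for 80% power at p = 0.05 to detect a 25% change in 12-month decline. Assume a two-sided, two-sample comparison with equal variances:

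- 25% of the decline = √2 × (1.960 + 0.842) / √66 = 0.488 SD
- full 12-month decline = 0.488 / 0.25 = 1.95 SD
- 6-month decline, if linear with the same SD = 1.95 / 2 = 0.975 SD

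With s = 0.3:

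| D | s − D | noncentrality | significant rise |
|---|---|---|---|
| 0.975 | −0.675 | −3.02 | below 0.0001% |
| 0.488 (half) | −0.188 | −0.84 | 0.3% |
| 0.244 (quarter) | +0.056 | +0.25 | 4.3% |

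If decline is near what the background implies, a false rise is negligible. The more plausible effect is a softened decline: a 0.3 SD shift would hide 0.3 / 0.975 = 31% of it. The lower tail of the same distribution gives the chance of a significant decline, which would fall from 98.5% (s = 0) to 81.7% (s = 0.3).

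The value of s comes from nowhere in the documents. It would be near zero for a fully automatic pipeline.

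**The case against.** **The contrast with the fluid assays is explained.** The blinding sentence directly follows the disclosure that a financially interested sponsor will do the laboratory work. The General section keeps the sponsor out of evaluating subjects, which takes place at the clinical site. A reader might infer that PET was overlooked under a general blinding policy, or that the financial conflict reaches the scans. The documents support neither. This part of the objection stands, and what remains is ordinary expectation bias.

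**The method leaves little discretion.** This is largely right for the cited mapping, and nothing in the plan describes handling by eye. It does not cover the added regional and hippocampal comparisons. There, the unlisted regions and the resulting multiplicity are a larger problem, which masking does not solve.

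**The direction is only partly written in.** The 2-FDG PET section opens with neutral wording, and the only formal hypothesis concerns isoprostanes. That is fair. Even so, the General section and the Conclusions look for a rise.

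**PET is exploratory, and masking does not supply a control group.** Both are true. They limit the weight of the point but do not remove it.

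**Conclusion.** The point holds in a limited form. Masking of time in study is written for serum and spinal fluid only. The PET comparisons can therefore be made with scan order known, in a study where everyone is treated. The consequence is a modest, unquantified risk of expectation bias that would soften a decline or favour a rise in an exploratory outcome. The safety conclusion does not depend on it.

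Two stronger readings are not supported:

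- **That the false-positive rate becomes 6%, 13% or 25%.** These figures recompute, but they rest on a test and alpha not stated for PET, an assumed shift, and zero underlying decline. The 66-per-arm figure implies about 1 SD of decline at six months, if linear. Figure 7 does show spared regions, so zero decline is possible somewhere, but the plan does not say that those are the regions to be compared.
- **That such a bias could never be found later.** Stored images can be coded and quantified again. Prevention is simply easier.

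This is a low-priority but worthwhile change.

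**What to change.** Add to the 2-FDG PET section:

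1. Technical quality control of each scan is done promptly at acquisition. This step must not wait for the second scan; otherwise a failed baseline scan would surface about six months into dosing, when no pre-treatment scan could be repeated.
2. The images are then stripped of date and time point and given a random code.
3. Registration, any exclusions from analysis and all regional values, including hippocampus, are completed and locked under the code.
4. The code is broken only after that lock, immediately before the before/after comparison and the correlation with isoprostane change.

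Cost: a little coding work by existing staff for about 40 scans (20 participants × 2), and quantification of each baseline scan waits until the second is available. Visits, sample size and participant burden do not change.

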The honest answer is that causes of regional vulnerability are both intriguing and remain elusive. Altering their mechanisms may offer great therapeutic benefits. Yet, rational experiments to alter pathogenic mechanisms can proceed in the absence of knowing how regional vulnerability occurs. In the case of AD and PD, overlapping of clinical phenotypes and pathologies with disease progression implicates similar disease mechanisms, at least in some subjects.

SPECIFIC AIMS

The primary aim of this protocol is to test the safety and tolerability of R-Pramipexole in humans with probable AD. We will also explore changes in oxidative stress and brain metabolic consequences as a "proof of concept" exploratory aim.

Primary Aim: Assess the safety and tolerability of R-Pramipexole in probable AD. Twenty subjects with probable AD will initiate treatment with 100 mg/day of R(+) pramipexole for one month. If tolerated, the subjects will increase to 200 mg/day for one month and then 300 mg/day for the next 4 months. Participants will be contacted by phone every two weeks to determine any adverse events. They will also be examined by a physician, have their vital signs measured and have routine safety blood labs performed every two months.

Exploratory Aim: Assess the effect of R-Pramipexole on oxidative stress and brain metabolic consequences. Prior to initiation of R(+)PPX dosing, we will obtain plasma and spinal fluid for oxidative stress markers and obtain brain glucose metabolism PET scans (2FDG PET). During the last month of 300 mg/day dosing, obtain plasma and spinal fluid samples and repeat 2FDG PET scan.

PRELIMINARY DATA

R(+)pramipexole is a mitochondrially concentrated antioxidant

Pramipexole (PPX) is a benzothiazole synthesized in the 1980's as an apomorphine analogue [27]. The stereospecific synthesis yielded S(-)PPX (Figure 1), which possessed potent and full agonist actions at the D2 family of brain dopamine receptors. S(-)PPX was developed for clinical use in humans and was approved in 1997 by the FDA as Mirapex®, for treatment of Parkinson's disease symptoms due to nigrostriatal dopamine deficiency.

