Study Drug Administration: R(+)PPX is provided by the sponsor to the KUMC investigational pharmacy as the water soluble dihydrochloride salt, in the form of powder manufactured under GMP conditions by Quality Chemical Laboratories, the supplier of drug for all of [name] studies. The investigational pharmacy prepares a water solution at 10 mg/ml. This solution has been tested by the sponsor and is stable at 4 degrees for at least two months.

Treatment is initiated after the Baseline visit at 100mg a day (50 mg bid in morning and early evening) for 1 month. If tolerated, dosing will increase to 200mg a day (100 mg bid) for a second one-month interval. If at the end of four months of being on study drug, the participant is not experiencing side effects the study drug will be increased to 300mg a day (150 mg bid) where it will remain for the next 4 months. Subjects will be seen every two months for safety assessments prior to any dose escalation and will also be contacted every two weeks by phone (see below). If a participant experiences mild, non-serious adverse events possibly due to the study drug, the study clinician will determine the causality and make a decision whether to continue the study medication and at what dosage. If study drug is discontinued temporarily (>10 days), it will be titrated to the target dose with dose increases no more frequent than once a month.

Drug Accountability: Participants in the study will return any unused drug and study drug containers at each of the safety visits. Study partners will be asked to account for any missed dosages of the study drug and the reason for missing the dosing. Participants are encouraged to maintain 100 percent compliance with dosing. The study partner and the participant will be advised of their

compliance at each safety visit before the study drug is dispensed and means and measures to increase compliance will be initiated. All unused study drug and containers will be returned to the investigational pharmacy for disposal.

Phone Calls: Participants and their study partner will be contacted by the study coordinator every two weeks by phone after starting to take the study medication to review concurrent medications and adverse events.

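### The dosing paragraph needs 32 weeks but treatment lasts 24, and the protocol reaches 300 mg/day at week 8 in one place and week 16 in two others

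*Combined protocol and SAP*

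**What the plan says.** Three places in the combined protocol and SAP describe the escalation.

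- **Specific Aims, Primary Aim.** One month at 100 mg/day, then "If tolerated, the subjects will increase to 200 mg/day for one month and then 300 mg/day for the next 4 months". The Exploratory Aim adds: "During the last month of 300 mg/day dosing, obtain plasma and spinal fluid samples and repeat 2FDG PET scan".
- **Treatment protocol, Study Drug Administration.** One month at 100 mg/day, after which "dosing will increase to 200mg a day (100 mg bid) for a second one-month interval". The next step is conditional: "If at the end of four months of being on study drug, the participant is not experiencing side effects", the dose goes to 300 mg/day, "where it will remain for the next 4 months". The paragraph also says "Subjects will be seen every two months for safety assessments prior to any dose escalation". After an interruption of more than 10 days, "it will be titrated to the target dose with dose increases no more frequent than once a month".
- **Conclusions.** Escalation from 100 to 300 mg/day is described as taking 4 months.

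The length of treatment is fixed elsewhere. The Overview and the safety analysis text put it at 6 months. End-of-Treatment Assessments places the final outcome measures and the return of all drug at week 24, with nothing further dispensed. The End-of-Study visit comes two weeks after treatment, and the schedule puts it at week 26. Drug is dispensed at Visits 1, 2 and 3 (weeks 0, 8 and 16). Between visits, participants are "contacted by the study coordinator every two weeks by phone". The schedule has no row for dose.

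**The concern.** The primary aim is safety and tolerability up to 300 mg/day, and the results are meant to guide dose selection for a later study. The paragraph that staff and pharmacy would work from cannot be carried out in the time available, and it disagrees with the Aims on when the target dose starts.

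The practical clash falls in weeks 8-16. The Aims call for 300 mg/day. The dosing paragraph limits 200 mg/day to one month and then names no dose until the end of month four. At Visit 2 the pharmacy has to dispense eight weeks of a 10 mg/ml solution without a single stated dose to work to.

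The choice also settles how much 300 mg/day experience lies behind the final safety findings, the second lumbar puncture and the second PET scan.

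**Working it through.** **Length of a month.** The Overview has safety visits every two months and the Safety Visits paragraph has them every 8 weeks, so 1 month = 4 weeks.

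**Stated treatment length.** Final visit at week 24; cross-check from the End-of-Study visit, 26 − 2 = 24 weeks.

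**Specific Aims.** 1 + 1 + 4 = 6 months = 4 + 4 + 16 = 24 weeks. This reproduces the stated length. 300 mg/day starts at week 8.

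**Study Drug Administration, read literally.** 4 months to the trigger + 4 months at 300 mg/day = 8 months = 32 weeks. Excess: 32 − 24 = 8 weeks. 300 mg/day starts at week 16. The named doses cover weeks 0-4 (100), 4-8 (200) and 16-32 (300), so weeks 8-16 have none. Carrying 200 mg/day forward fills that interval but goes against the one-month limit, and the total is still 32 weeks.

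**Conclusions.** 300 mg/day is reached at 4 months = week 16. This text does not itself require 32 weeks.

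| Schedule | 300 mg/day starts | Weeks at 300 by week 24 | Total length |
|---|---|---|---|
| Aims (1+1+4 months) | week 8 | 24 − 8 = 16 | 24 weeks |
| Dosing paragraph, literal | week 16 | 24 − 16 = 8 | 32 weeks |
| Two-month steps (2+2+2 months) | week 16 | 24 − 16 = 8 | 24 weeks |

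**Share of treatment at 300 mg/day.** 16/24 = 67% or 8/24 = 33%.

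**Cumulative dose by week 24.** Aims: 7 × (4×100 + 4×200 + 16×300) = 42,000 mg. Dosing paragraph, with 200 mg/day assumed through weeks 8-16 and stopping at week 24: 7 × (4×100 + 12×200 + 8×300) = 36,400 mg.

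**Visit 2 supply, eight weeks at 10 mg/ml.** 56 × 300/10 = 1,680 ml, or 56 × 200/10 = 1,120 ml.

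**Timing of the repeat samples and PET.** The last month at 300 mg/day is weeks 20-24 under either 24-week schedule, matching the week-24 assessments. Under the literal dosing paragraph it is weeks 28-32, after the drug has been returned. This rules out the 32-week reading but does not choose between the other two.

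**Calendar months (4.348 weeks each).** Dosing paragraph: 8 × 4.348 = 34.8 weeks. Aims: 6 × 4.348 = 26.1 weeks, so the Aims fit 24 weeks exactly only with 4-week months. Time at 300 mg/day by week 24: 24 − 8.7 = 15.3 weeks against 24 − 17.4 = 6.6 weeks. The conflict remains.

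**The case against.** The strongest reply is that four months may be no slip at all. Two-month steps, with 100, 200 and 300 mg/day from weeks 0, 8 and 16, fit four features: the four-month trigger, the 4-month escalation in the Conclusions, the clause that puts an in-person assessment before escalation, and dispensing at Visits 1, 2 and 3, one per dose. They also total 24 weeks. In a safety study the slower titration is the more cautious choice.

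Much of this stands: the documents do not settle the intent. Against it, the Aims and the dosing paragraph both state one-month steps and four months at 300 mg/day. The PET analysis text and the Conclusions both expect several months at 300 mg/day before the repeat scan, which 16 weeks fits better than 8. The re-titration rule contemplates increases as often as monthly, though it sets only a minimum spacing. Monthly steps are the better supported reading, not the only one.

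Three stronger readings are tempting and not supported:

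- A reader might infer that staff have no dose for a third of treatment. That is true only of the dosing paragraph in isolation. The Aims give 300 mg/day for those weeks, and an increase to 300 mg/day implies that 200 mg/day continues until then. The problem is two competing doses.
- A reader might infer that the monthly step at week 4, when only a phone call is scheduled, breaches a required visit. That depends on whether the every-two-months clause sets a condition for escalation or only a visit cadence, and the wording allows both.
- A reader might infer a risk of overdosing. No reading exceeds 300 mg/day, and the two-weekly calls, quarterly DSMB review and grade 3 rules apply under all of them.

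**Conclusion.** The point holds. The dosing paragraph is 8 weeks too long for the treatment period, and the protocol gives two start times for 300 mg/day, week 8 and week 16. Maximum exposure at the target dose before the week-24 assessments is 16 or 8 weeks, a factor of two, for participants who complete every step on time.

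The week counts rest on 4-week months; calendar months change the figures but not the conclusion. The sentences concerned are complete, so neither redaction nor text extraction explains the conflict.

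This is an internal inconsistency in an operative instruction, and it should be corrected before dosing under the protocol. Confidence is high for the contradiction and moderate for monthly steps as the intended schedule.

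**What to change.** Unless the sponsor and investigator say that two-month steps were meant:

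- In Study Drug Administration, change the trigger for 300 mg/day from four months to two.
- In the Conclusions, change the escalation period from 4 months to 2.
- Add a dose row to the schedule: 100, 200 and 300 mg/day from weeks 0, 4 and 8, with 300 mg/day to week 24.
- State that the step to 300 mg/day follows the Visit 2 (week 8) examination and safety labs.

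If two-month steps were intended, amend the Specific Aims and the dosing paragraph to 2 + 2 + 2 months, put weeks 0, 8 and 16 in the dose row, and acknowledge that 300 mg/day is then observed for 8 weeks.

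Under monthly steps the sponsor must also decide how the clause on assessment before escalation applies at week 4, where only a call is scheduled. Whether a call is enough or a visit is needed is a safety judgement that this correction does not make. The caregiver would also need an instruction to change the volume at home, from 5 ml to 10 ml twice daily at 10 mg/ml (50 mg to 100 mg per dose).

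The cost is a wording amendment to two sections, one added sentence and one calendar row, with no new visits. A week-4 visit, if the sponsor wants one, would add up to 20.
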